### **7.3.2. Missing Data**

The primary efficacy endpoint is the percent of subjects with  $\geq 15$  letters of improvement in photopic binocular DCNVA and with  $< 5$  letters of loss in photopic binocular BCDVA from Baseline comparing Nyxol-treated subjects to placebo-treated subjects at 12 hours post-dose at Visit 2 (Stage 1 Day 8). For the analysis of the primary efficacy and key secondary endpoints, imputation will be performed for missing efficacy data as specified in Section 7.3.2.3 for the analysis using the mITT, as well as either PP population, if required. Confirmatory analyses may be performed using the ARP, also using imputation for missing data.

Otherwise, there will be no substitutions made to accommodate missing data points for efficacy data. All data recorded on the CRF will be included in data listings that will accompany the CSR.

Safety data will be imputed in limited situations. If the severity of an AE is missing, then the severity will remain missing. If relationship of the AE to study drug is missing, the relationship will remain missing. Missing or partial dates for AEs or concomitant medications will be imputed as described in Section 7.3.2.1. Otherwise, all summaries of safety endpoints will be completed using observed cases in the SP; no imputation will be completed.

#### **7.3.2.1. Handling of Missing Date Values**

##### Partial or Missing Dates

The following conventions will be used to impute missing portions of dates for AEs and concomitant medications, if warranted. Note that the imputed values outlined here may not always provide the most conservative date. In those circumstances, the imputed value may be replaced by a date that will lead to a more conservative analysis.

A. Start Dates

- 1) If the year is unknown, then the date will not be imputed and will be assigned a missing value.
- 2) If the month is unknown, then:
  - i) If the year matches the first dose date year, then impute the month and day of the first dose date.
  - ii) Otherwise, assign 'January.'
- 3) If the day is unknown, then:
  - i) If the month and year match the first dose date month and year, then impute the day of the first dose date.
  - ii) Otherwise, assign the first day of the month.

B. Stop Dates

- 1) If the year is unknown, then the date will not be imputed and will be assigned a missing value.
- 2) If the month is unknown, then assign 'December.'
- 3) If the day is unknown, then assign the last day of the month.

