#### *Stage 1: Dosing of Treatment 1*

Individuals who are potential subjects are identified by the study center to schedule the Screening Visit. If a subject successfully completes their Screening Assessments, then Visit 1 becomes the Baseline Visit.

Once a subject arrives at the study center, a member of the Site Staff interviews the individual as to their qualifications for participation in the study, and if the subject wishes to continue, the informed consent form (ICF) is signed, and a subject number is assigned.

If all eligibility criteria are met, the subject is randomized into the study.

At Visit 1 (Stage 1 Day 1), eligible subjects were randomized, and the first dose of Treatment 1 was administered at the study site at Time 0 min (note: if Visit 1 is split into 2 separate days, then dosing occurs on the second day). Efficacy and safety measurements were made before dosing with Treatment 1 (Time 0 min) and at multiple post-dose timepoints from 30 min to 8 hours.

In Stage 1, the safety and efficacy of Nyxol as a single agent was evaluated after 1 day and 7 days of daily dosing.

Following Visit 2 (Stage 1 Day 8), subjects discontinued dosing Treatment 1 for 7 to 14 days (Washout Period). During the Washout Period, subjects returned for Visit 3 (Stage 1 Day 10  $\pm$  1 day) to assess the resolution of drug treatment effects.

During Stage 1, Treatment 1 is dosed daily in the evenings near bedtime starting with the day after completion of Visit 1, except for Visit 1 [Stage 1 Day 1], when the subject is dosed during the day at the study site, and the evening before Visit 2, when Treatment 1 is dosed as close to 12 hours prior to Time 0 min at Visit 2.

Analysis will consist of comparison across the 2 arms:

- Nyxol
- Placebo

*Stage 2: Dosing of Treatments 1 and 2*

Visit 4 (Stage 2 Day 1) is the start of Stage 2. In Stage 2, the efficacy and safety of Nyxol + LDP was evaluated following 1 day and 7 days of dosing, in which Treatment 1 (Nyxol or placebo) is dosed daily in the evenings near bedtime, except the evening before Visits 4 and 5, when Treatment 1 is dosed as close to 12 hours prior to the scheduled time for those visits. Treatment 2 (LDP or LDP vehicle) is dosed daily in the mornings. Treatment 2 will be dosed at the study site at the beginning of Visits 4 and 5 (Stage 2 Days 1 and 8, respectively).

Analysis consists of comparison across the 4 arms:

- Nyxol + LDP
- Nyxol + LDP vehicle
- Placebo + LDP
- Placebo + LDP vehicle

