### **10.1. Adverse Events**

AEs will be coded using MedDRA, Version 25.1.

Treatment-emergent adverse events (TEAEs) are defined as any AE that begins or worsens after initiation of the investigational product and through the subject's last study visit (study completion or early termination).

If the onset of an AE is on or after the date of first dose of study medication or is increasing in severity after first dose of study medication, then the AE will be considered treatment emergent.

Only TEAEs will be summarized; all AEs (TEAE, non-TEAE) will be included in a by-subject listing.

TEAEs that start during Stage 1 will only be counted in the Stage 1 tables using the Treatment 1 that was actually taken, regardless of the TEAE stop date. TEAEs that start during Stage 2 will be counted in both Stage 1 and Stage 2 tables.

The number and percent of subjects with any TEAEs will be summarized by SOC and PT by treatment group and overall. At each level of tabulation (e.g., at the PT level), subjects will be counted only once if they had more than one such event reported during the AE collection period.

Note that in MedDRA, ocular events are coded to the SOC of "Eye Disorders". Thus, using SOC in the summaries will provide a separation of ocular and non-ocular adverse events.

The following summary tables will be presented for TEAE data:

- Overall summary of TEAEs (completed for both the SP and mITT population)
- Summary table of TEAEs by SOC and PT
- Summary table of TEAEs by SOC, PT, and by greatest relationship level to study drug (not related, unlikely related, possibly related, probably related, definitely related, or unknown)
- Summary table of TEAEs by SOC, PT, and maximum severity (mild, moderate, severe)

- Summary table of serious TEAEs by SOC and PT
- Summary table of TEAEs leading to withdrawal from the study by SOC and PT
  
- Summary table of TEAEs leading to study medication discontinuation by SOC and PT

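### The partial-date rule dates most Stage 2 adverse events with an unknown start day before Visit 4, so they drop out of the four-arm Stage 2 tables

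*SAP*

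**What the plan says.** SAP 7.3.2 makes the date rules binding for adverse events: "Missing or partial dates for AEs or concomitant medications will be imputed as described in Section 7.3.2.1". For start dates, SAP 7.3.2.1 then provides:

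- Month unknown (rule 2(i)): "If the year matches the first dose date year, then impute the month and day of the first dose date".
- Day unknown, same month as first dose (rule 3(i)): "If the month and year match the first dose date month and year, then impute the day of the first dose date".
- Day unknown, any other month (rule 3(ii)): "Otherwise, assign the first day of the month".
- A general override for imputed dates that are not the most conservative: "In those circumstances, the imputed value may be replaced by a date that will lead to a more conservative analysis".

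SAP 10.1 assigns events to tables by start date: "TEAEs that start during Stage 1 will only be counted in the Stage 1 tables using the Treatment 1 that was actually taken". The next sentence adds: "TEAEs that start during Stage 2 will be counted in both Stage 1 and Stage 2 tables". SAP 5.1 fixes the boundary: "Visit 4 (Stage 2 Day 1) is the start of Stage 2". Protocol 5.5 puts Visit 4 on Day 15 to 22 and Visit 5 on Day 22 to 29. The legible text has no anchor at Visit 4 and no separate rule for assigning stage when a start date is imputed.

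**The concern.** An early imputed date is cautious when the question is whether an event is treatment-emergent. In this trial the start date also decides whether an event enters the Stage 2 tables, and for that question an early date is not cautious. The first dose always lies in Stage 1, and the 1st of the onset month usually precedes Visit 4. A true Stage 2 event with an unknown day is therefore usually dated to Stage 1.

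The Stage 2 tables are where the four arms are compared. The Stage 1 tables have only Nyxol and placebo columns, so an event confined to them cannot be seen as arising on pilocarpine or on its vehicle. The primary objective concerns the combination, so understating Stage 2 incidence matters even if few events are involved.

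**Working it through.** The plan gives no figure for misdated events, so there is none to reproduce. The check applies rules 3(i) and 3(ii) to the calendar.

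**Inputs.** Visit 4 on Day 15 to 22, with Visit 5 seven days later (Protocol 5.5). Stage 2 starts at Visit 4 (SAP 5.1). Assumptions: first doses spread evenly over a 365-day year, Visit 4 day uniform in its window, true onset uniform from 0 to 7 days after Visit 4, month and year known, day unknown.

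**Three examples.**

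| First dose | Visit 4 | True onset | Recorded | Imputed | Stage |
|---|---|---|---|---|---|
| 5 June | 22 June (Day 18) | 25 June | June | 5 June, rule 3(i) | 1 |
| 20 June | 4 July (Day 15) | 8 July | July | 1 July, rule 3(ii) | 1 |
| 14 June | 28 June (Day 15) | 2 July | July | 1 July, rule 3(ii) | 2 |

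**Share keeping a Stage 2 date.** An event stays in Stage 2 only if the 1st of a month falls on a day from Visit 4 to onset. With onset k days after Visit 4 there are k + 1 such days, and 12 of 365 days are the 1st of a month:

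- kept(k) = 12(k + 1)/365
- the mean of k + 1 over k = 0 to 7 is 4.5, so kept = 12 × 4.5/365 = 14.8%
- dated before Visit 4 = 100% − 14.8% = **85.2%**

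**Split by rule.** Rule 3(i) applies when no month boundary lies between first dose and onset. The mean gap is 17.5 + 3.5 = 21 days, so the share is 1 − 12 × 21/365 = 31.0%. Rule 3(ii) supplies the rest: 85.2% − 31.0% = 54.2%. Both rules are needed to reach a majority.

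Day-by-day enumeration over the 2023 calendar gives the same figures. A nine-month accrual (assumed start 1 December 2022) gives 85.0%.

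**Sensitivity** (% of true Stage 2 events with unknown day that are dated to Stage 1).

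| Scenario | Rule 3(i) | Rule 3(ii) | Total |
|---|---|---|---|
| Base case | 31.0 | 54.2 | 85.2 |
| Visit 4 always Day 15 | 42.5 | 42.7 | 85.2 |
| Visit 4 always Day 22 | 19.5 | 65.8 | 85.2 |
| Visit 4 on Day 9–16 (Protocol 8.3 wording) | 50.7 | 34.5 | 85.2 |
| No onsets on the Visit 4 day | 29.3 | 54.2 | 83.6 |
| All onsets on the Visit 4 day | 42.5 | 54.2 | 96.7 |
| All onsets on the Visit 5 day | 19.5 | 54.2 | 73.7 |
| Stage 2 taken to start the evening before Visit 4 | 31.0 | 51.0 | 81.9 |
| Day 22, all onsets on the Visit 5 day, evening-before start | 7.9 | 62.5 | 70.4 |

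Some rows do not add exactly because of rounding. With the month unknown the share is 98.8%, but that is an unlikely gap for an event within one week.

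**Scale (illustration only).** Protocol 3.2 reports TEAEs in 15 subjects (34.1%, so about 44 treated) on the combination in the earlier study, and in 4.4% on placebo alone. In an arm of about 80, 80 × 15/44 = 27.3 subjects. Let u be the share with an unknown start day and no other Stage 2 event. The number lost is 27.3 × u × 0.852:

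| Assumed u | Subjects lost of 80 |
|---|---|
| 1% | 0.2 |
| 5% | 1.2 |
| 10% | 2.3 |
| 20% | 4.6 |

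One subject is 1/80 = 1.25 percentage points. If u is the same in every arm, each incidence is multiplied by 1 − 0.852u. At u = 5% the factor is 0.957, and the earlier study's difference of 34.1 − 4.4 = 29.7 points becomes 28.4. At u = 20% the factor is 0.830, and it becomes 24.6.

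**The case against.** Five points can be made for the plan.

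- **The override covers it.** In part. It allows a more conservative date, but it is optional and does not say what conservative means for stage. Left as it is, replacement would be a case-by-case choice.
- **Partial dates should be rare.** This stands. Stage 2 lasts about a week between two 8-hour clinic visits. Protocol 9.3 and 9.3.1 require a start date and questioning about events at each visit, and Protocol 5.7 adds edit checks and source review. The documents give no rate of partial dates. SAP 10.1 also counts a subject once per level, so a lost event matters only if the subject has no other Stage 2 event at that level.
- **The events do not disappear.** This stands. They remain in the Stage 1 tables and the by-subject listing. A reader might infer that the imputation wrongly moves them to Nyxol or placebo alone. The documents do not support that, because correctly dated Stage 2 events are counted in the Stage 1 tables as well. The only change is omission from the Stage 2 tables.
- **No arm is favoured.** This stands as far as it goes. A reader might infer that the rule is tilted towards the combination, but it is blind to treatment and acts alike in all four arms. Absolute differences still shrink.
- **A stage-specific rule can err the other way.** This also stands: true Stage 1 or washout events with an unknown day could be dated to Stage 2.

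**Conclusion.** The point holds as a defect in a stated rule, with a modest likely effect. Followed as written, rules 3(i) and 3(ii) together remove about 85% of true Stage 2 events with an unknown start day from the four-arm tables. The range is 70% to 97% over the onset patterns, visit windows and stage boundaries tried. The total does not depend on when Visit 4 falls within its window. It depends on how soon after Visit 4 events begin and on where the Stage 2 boundary is drawn.

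The percentage applies only to events with a partial date. Their number cannot be derived from the documents and is probably small, so no claim of a large distortion is supported. The result is lower Stage 2 incidence in every arm and smaller absolute differences. It is worth correcting before unmasking because the remedy is simple and the rule bears on the safety comparison for the primary treatment.

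**What to change.** Add to SAP 7.3.2.1, for assigning stage only:

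- If the known parts of an adverse event start date are compatible with onset on or after Visit 4, impute the later of the Visit 4 date and the earliest date those parts allow.
- Do not do this if a known stop date, or the visit at which the event was first reported, shows earlier onset.
- Never impute a start after a known stop date.

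The anchor should be the Visit 4 date, which is the SAP's start of Stage 2 and the day of the first Treatment 2 dose. The first Stage 2 dose of any kind would not serve: Protocol 3.5 and 5.4.4 restart Treatment 1 the evening before Visit 4, so the same 85.2% would still be dated before Visit 4. With the Visit 4 anchor, and where neither exception applies, no imputed date precedes Visit 4 and the share falls to 0%.

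SAP 10.1 should also state whether events starting between that evening dose and Visit 4 belong to Stage 1 or Stage 2.

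The cost is a few sentences and minor programming. The downside is that some true Stage 1 or washout events with an unknown day may enter the Stage 2 tables; the stop-date and reporting-visit conditions limit this. The Stage 1 tables lose nothing, because Stage 2 events are counted there too.

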7.3.2.2. Missing Baseline Data

Every effort will be made to ensure that accurate baseline information on the subjects is collected. In the event that a subject is missing baseline information that is required for the primary efficacy analyses, the subject will be included in the SP for assessment of safety and excluded from the primary analyses. Each case of missing baseline data will be evaluated for potential inclusion in the exploratory endpoints. All baseline data will be observed cases, without imputation.

7.3.2.3. Imputation Methods

### **7.3.3. Handling of Early Termination Visit Information**

In the event that a subject is terminated early from the study, the early termination data will be assigned to the closest scheduled visit and/or time point. If the closest visit or time point has valid data, the early termination data will be assigned to the next available visit or time point.

### **7.3.4. Pooling of Investigational Sites**

The data from all study centers will be pooled together for all planned analyses.

### **7.3.5. Coding Conventions for Events and Medications**

All AEs and medical history will be mapped to the Medical Dictionary for Regulatory Activities (MedDRA Version 25.1) system for reporting (preferred term and body system).

Prior and concomitant medications will be coded using WHO-DD (World Health Organization Drug Dictionary) (Version Global C3, September 1, 2022).

### **7.3.6. Analysis Software**

Data manipulation, tabulation of descriptive statistics, calculation of inferential statistics, and graphical representations will be performed primarily using SAS (release 9.4 or higher) for Windows. If the use of other software is warranted, the final CSR will detail what software was used and for what purposes.

### **7.3.7. Study Data**

[figure not shown]
**Study data identified in the schedules for time and events (**

Table 1 and Table 2) are collected, and source verified, on the electronic data capture (EDC) Fountayn Version 1.0.0.

All study data will be formulated into regulatory-compliant data sets to provide transparency, traceability, and integrity of trial analysis results from the collection source. Observed study data will be mapped to the Clinical Data Interchange Standards Consortium (CDISC) Study Data Tabulation Model (SDTM) and serve as the source data from the trial. All study analyses will be completed using analysis data sets that are derived from the SDTM and follow the CDISC Analysis Data Model (ADaM) architecture.

The methods for programming the CDISC SDTM and ADaM data sets are described in Figure 1.

**Figure 1** SDTM, ADaM, and TFL Development and Validation

[REDACTED]

## **7.4. Planned Study Analyses**

### **7.4.1. Statistical Summaries: Descriptive and Inferential**

Categories for data presentation and analysis will consist of each treatment group: Nyxol and placebo for Stage 1, and Nyxol + LDP, Nyxol + LDP vehicle, Placebo + LDP, and Placebo + LDP vehicle for Stage 2.

All statistical tests will be two-sided and a difference resulting in a p-value of less than or equal to 0.05 will be considered statistically significant. The p-values for the analysis of secondary efficacy endpoints and safety endpoints will be considered descriptive, unless the endpoint is used for the hierarchical testing method. All p-values will be rounded to and displayed in four decimals. If a p-value less than 0.0001 occurs, it will be shown in tables as <0.0001.

Descriptive summaries of variables will be provided where appropriate. For continuous variables, the number of non-missing values (n), mean, standard deviation, median, minimum, and maximum will be tabulated by treatment group. For categorical variables, the counts and proportions of each value will be tabulated by treatment group. Expansion of descriptive table categories within each treatment may occur if such elaborations are thought to be useful.

All study-related data collected will be presented in listings. Study-related data not subject to analysis according to this plan will not appear in any tables or graphs but will be included in the data listings.

### **7.4.2. Interim Analyses and Data Monitoring**

No formal interim analysis or safety monitoring committee is planned for this study.

### **7.4.3. Final Analysis and Publication of Study Results**

The final analysis will be completed after all subjects have completed the study.

## **7.5. Multiple Testing Procedures**

A hierarchical analysis will formally test a family of endpoints beyond the primary efficacy endpoint. The percent of subjects with  $\geq 15$  letters of improvement in photopic binocular DCNVA and with  $< 5$  letters of loss in photopic binocular BCDVA will be analyzed at 30 min post-LDP/vehicle at Visit 5 (Stage 2 Day 8 [Day 22-29]), comparing Nyxol + LDP to placebo + LDP vehicle, Nyxol + LDP vehicle, and placebo + LDP. These comparisons will be analyzed second, third, and fourth in the testing hierarchy. The full hierarchy is in Section 12.3.

Otherwise, there will be no adjustments for multiplicity and no formal multiple testing procedures are to be implemented with this analysis plan.

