## **10.3.5.** Analysis of Efficacy

Efficacy will be assessed using the mITT and PP Populations, with subjects included in the treatment arm into which they were randomized. For the analysis of the primary efficacy endpoint, appropriate imputation techniques will be performed for missing observations if applicable; details will be provided in the study SAP. The primary comparison of interest is Stage 2 Nyxol + LDP versus placebo + LDP vehicle for the mITT Population. Confirmatory analyses may be performed using the ARP, with imputation performed for missing data. For the analysis of the secondary efficacy endpoints, only observed case data will be used. If warranted,

confirmatory analyses using the ARP with imputation for missing data will also be performed for the secondary efficacy endpoints.

For all efficacy endpoints, Baseline values are defined as the latest values taken prior to administration of Treatment 1, which will usually be the screening assessment values on Visit 1.

All efficacy data will be summarized by treatment group, study visit, and timepoint, as appropriate.

The primary efficacy endpoint is the percent of subjects with  $\geq 15$  letters of improvement in photopic binocular DCNVA and with < 5 letters of loss in photopic binocular BCDVA at 30 min post-LDP/vehicle comparing Nyxol + LDP to placebo + LDP vehicle at Visit 5 (Stage 2 Day 8).

The primary efficacy endpoint will be

as a covariate. The percentage of subjects in each

treatment arm meeting the criteria, the odds ratio (OR) with 95% confidence interval (CI), and pvalue will be provided. The analysis will be performed using the mITT and PP Populations, with subjects included in their randomized treatment regardless of the treatment they actually received. A sensitivity analysis will be completed for the primary efficacy endpoint using the same model but excluding the light/dark irides factor.

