#### *Primary objective*

- To evaluate the efficacy of LDP as adjunctive therapy to Nyxol (Nyxol + LDP) to improve DCNVA without loss of BCDVA compared to placebo + LDP vehicle in subjects with presbyopia

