### 4.2. Study Endpoints

#### 4.2.1. Primary Endpoints

The primary efficacy endpoint is the percent of subjects with  $\geq 15$  letters of improvement in photopic binocular DCNVA and with  $< 5$  letters of loss in photopic binocular BCDVA from Baseline at 30 min post-LDP/vehicle comparing subjects treated with Nyxol + LDP to subjects treated with placebo + LDP vehicle at Visit 5 (Stage 2 Day 8).

This comparison will be analyzed first using a hierarchical testing method.

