## **7.3. Management of Analysis Data**

### **7.3.1. Data Handling**

Data from unscheduled visits may be used for the primary efficacy analysis as described in Section 7.3.2.3 below. Otherwise, unscheduled visit data will not be included in the analysis of efficacy or safety but will be listed.

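### SAP 7.5 ranks the primary comparison no earlier than second, while SAP 4.2.1 and three Protocol sections test it first; SAP 7.3.2 still defines the superseded Visit 2 primary

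*SAP*

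**What the plan says.** **Places that put the primary first.** SAP 4.2.1 defines the primary endpoint as the responder rate (a gain of at least 15 letters in DCNVA with a loss of fewer than 5 letters in BCDVA) at 30 minutes post-LDP/vehicle, Visit 5, for Nyxol + LDP against placebo + LDP vehicle. It adds: "This comparison will be analyzed first using a hierarchical testing method". The Protocol synopsis, 5.1 and 8.1 carry the same sentence. Protocol 10.3.5 agrees on the contrast: "The primary comparison of interest is Stage 2 Nyxol + LDP versus placebo + LDP vehicle for the mITT Population". So does the primary objective in SAP 4.1 and Protocol 4: "to improve DCNVA without loss of BCDVA compared to placebo + LDP vehicle in subjects with presbyopia".

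**The place that puts it later.** SAP 7.5 opens with "A hierarchical analysis will formally test a family of endpoints beyond the primary efficacy endpoint". It then names the same responder endpoint at 30 minutes, Visit 5, with Nyxol + LDP compared to placebo + LDP vehicle, to Nyxol + LDP vehicle and to placebo + LDP. It continues: "These comparisons will be analyzed second, third, and fourth in the testing hierarchy". For the rest it refers onward: "The full hierarchy is in Section 12.3". That section is redacted.

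**The leftover definition.** SAP 7.3.2 describes the primary endpoint as "comparing Nyxol-treated subjects to placebo-treated subjects at 12 hours post-dose at Visit 2 (Stage 1 Day 8"). Yet SAP 3.1 names Amendment 3 as the reference protocol, and SAP 3.3 declares the SAP's analyses consistent with the protocol.

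**The concern.** The order of tests is the only multiplicity control that the visible SAP provides. SAP 7.4.1 treats secondary p-values as descriptive unless the endpoint belongs to the hierarchy, and 7.5 rules out any other adjustment. The stated order therefore decides which results are formal. A pivotal SAP that gives its primary test two different ranks leaves that decision open to choice once data are seen.

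The two faulty SAP passages also fit together. Three comparisons take ranks two to four in 7.5, which names no specific contrast for rank one, and 7.3.2 still calls the Visit 2 single-agent comparison primary. Read together, they describe a coherent but outdated plan with the Visit 2 test in front. If that were the operative order and the hierarchy is a fixed sequence, a failed Visit 2 test would block a formal claim on the current primary. Under SAP 4.2.1 nothing stands ahead of it.

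One visible rule also depends on which analysis is primary. SAP 7.3.1 states: "Data from unscheduled visits may be used for the primary efficacy analysis as described in Section 7.3.2.3 below"; otherwise unscheduled data are excluded.

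**Working it through.** **1. Rank of Nyxol + LDP against placebo + LDP vehicle, 30 minutes, Visit 5**

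| Place | Rank given |
|---|---|
| SAP 4.2.1 | first |
| Protocol synopsis | first |
| Protocol 5.1 | first |
| Protocol 8.1 | first |
| SAP 7.5 | second if the list order is followed; second to fourth on any reading |

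These are all operative sections, not the amendment log.

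**2. Can 7.5 be read so that it agrees with 4.2.1?** There are two candidates for rank one.
- Rank one is the 4.2.1 primary. The same contrast then appears again among ranks two to four, so the list in 7.5 is wrong.
- Rank one is the Visit 2 comparison that 7.3.2 calls primary. Then 4.2.1 and the three Protocol sections are wrong.

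Neither leaves the text consistent.

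**3. Does the redacted Section 12.3 settle it?** If it puts the primary first, it contradicts 7.5. If it does not, it contradicts 4.2.1. A visible section needs editing in both cases.

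**4. What a Visit 2 gate would cost.** This is conditional: neither the gate nor a fixed-sequence rule is visible.

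Inputs:
- Two-sided alpha 0.05 (SAP 7.4.1).
- 300 evaluable subjects, 150 each on Nyxol and placebo (Protocol synopsis). Split over four equal arms, 300/4 = 75.
- Phase 2 rates from Protocol 3.2: 30.1% vs 13.5% (Nyxol alone, 12 hours) and 60.45% vs 27.9% (Nyxol + LDP, 1 hour).

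The plan's own power calculation cannot be reproduced, because its rates and power are not visible.

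Formula: power = Φ{[|p1 − p2| − 1.96·√(2p̄(1 − p̄)/n)] / √[(p1(1 − p1) + p2(1 − p2))/n]}, with p̄ the mean of p1 and p2.

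- Gate, n = 150: p̄ = 0.218; (0.166 − 1.96 × 0.04768)/0.04670 = 1.554; power **94.0%**.
- Primary, n = 75: p̄ = 0.44175; (0.3255 − 1.96 × 0.08109)/0.07661 = 2.174; power **98.5%**.

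Chance that both succeed:
- independent: 0.940 × 0.985 = 92.6%
- lower bound under any dependence: 0.940 + 0.985 − 1 = 92.5%
- upper bound: min(0.940, 0.985) = 94.0%

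The loss against 98.5% is therefore 4.5 to 6.0 percentage points.

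**5. If the single-agent effect is smaller than in phase 2.** The gate's own power, at 150 per arm, caps the chance of a formal primary claim:

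| Assumed Nyxol vs placebo | Gate power |
|---|---|
| 30% vs 15% | 87.9% |
| 25% vs 13.5% | 71.6% |
| 25% vs 15% | 58.2% |

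Averaging over phase 2 sampling error gives one summary. The only counts with denominators from 66 to 81 that round to the printed percentages are 22/73 and 10/74. With Beta(22.5, 51.5) and Beta(10.5, 64.5) and 400,000 draws, the gate succeeds 81% of the time and fails about 19%.

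**The case against.** The strongest reply is that 7.5 contains a clerical slip with an obvious answer. Its opening sentence takes the primary endpoint as the starting point, SAP 4.2.1 is where endpoints are defined, and four places say first against one. On that reading 7.5 merely repeats the primary contrast, which costs no alpha and gates nothing. The order is also deferred to a redacted section, and redacted text is not missing from the plan.

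Much of this is fair. Incomplete editing after Amendment 3 is the likeliest cause, and a Visit 2 gate is not shown. But the benign reading concedes that 7.5 is wrong as written, and step 3 shows that the redaction cannot rescue it.

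The power figures have real limits:
- Both phase 2 pairs lack the BCDVA condition.
- The single-agent rates follow 3 to 4 days of dosing, where Stage 1 here runs for 7.
- The combination pair is per-protocol at 1 hour, and its control was placebo alone.
- The primary analysis is mITT with imputation, so up to about 160 and 80 per arm could count. Powers are then 95.3% and 99.0%, and the loss 3.7 (99.0 − 95.3) to 4.7 (100 − 95.3) points.

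The figures illustrate the stakes only.

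Two side points are minor. No effect of the 7.3.2 leftover on imputation is shown, because that section treats primary and key secondary endpoints alike; and the text of 7.3.2.3, on which the unscheduled-visit rule relies, is not visible. The Protocol 8.2.5 note calling the 30-minute measurements key secondary is incomplete, not false.

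**Conclusion.** The concern stands and must be fixed before unmasking. The visible SAP gives its one primary test two incompatible ranks, and a live section still defines the primary as the superseded Visit 2 comparison. Confidence is high for those two statements, which rest only on current text.

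That another test precedes the primary remains a possibility. If one did, as a Visit 2 gate in a fixed sequence, the loss would be about 4.5 to 6 points at the phase 2 rates with 150 and 75 per arm, and larger if Nyxol alone does less well than in phase 2. None of this shows that the trial is underpowered. The severity comes from the contradiction about the confirmatory test, not from those conditional figures.

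**What to change.** 1. **SAP 7.5:** state that Nyxol + LDP against placebo + LDP vehicle at 30 minutes, Visit 5, is tested first, followed by the comparisons with Nyxol + LDP vehicle and with placebo + LDP. Confirm that Section 12.3 gives the same order, with nothing ahead of the primary.
2. **SAP 7.3.2:** replace the Visit 2 definition with the endpoint as defined in 4.2.1.
3. **Protocol 8.2.5:** let the note say that the 30-minute Visit 5 measurement serves the primary endpoint as well as key secondary ones.

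Items 1 and 2 are the substance and need only SAP wording. SAP 3.1 already requires the SAP to be final before unmasking; a correction made by then cannot be called data-driven. Item 3 is minor, but Protocol 13.3 makes any protocol change an approved amendment with FDA submission and IRB approval, so it carries that administrative cost. None of the three needs extra subjects, visits or data.
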